11. PROCEDURES INVOLVED*

For **Aim 1**, the design thinking workshops are described in the grant application under “RESEARCH PLAN” (p.9-10).

For **Aim 2**, participants will be recruited from UMMHC EDs. This will include patients (n~12) and their treating physicians or behavioral health clinicians (n~4). See grant: “RESEARCH PLAN” (p.10) for details on the procedure. We will collect the following:

- Patient case report form, for demographics, psychiatric and suicide history, familiarity with mobile phone/computing technology, self-efficacy/capability
- System Usability Scale (SUS)
- User Engagement Scale (UES)

The second half of these participants (Cycle 2) will also be invited to download the app to their smartphone and followed up to obtain these usability measures again one week after ED discharge (“Cycle 2”, RESEARCH PLAN, p.10). Participation will not affect their care, see grant: “HUMAN PARTICIPANTS PROTECTIONS” (p.19-20).

Aim 3 is a pilot randomized controlled trial of 45 ED patients who screened positive during triage for recent active suicidal ideation or suicide attempt. They will be recruited from UMMHC EDs. They will be randomized to one of three TASCS App modalities in the ED (in-person clinician, telehealth clinician, self-directed). All three groups will receive three

INVESTIGATOR STUDY PLAN - TASCS

counseling calls, access to the TASCS app, and one assessment call in the three months after discharge. See grant: “RESEARCH PLAN” (p.11-13) for details on the procedure. Participation will not affect their care see grant: “HUMAN PARTICIPANTS PROTECTIONS” (p.19-20). Measures to be included are:

Measures at baseline and follow-up in feasibility trial (Aim 3)

Construct	Measure
Initial implementation measures	
Usability	System Usability Scale
Acceptability	Qualitative feedback
	Technology Acceptance Model Scale
	User Engagement Scale
Patient-level outcomes	
Suicidal ideation and behavior	Columbia Suicide Severity Rating Scale ;suicide-related ED visits
Intervention targets	
Behavioral activation/effort	Drive subscale of the Behavioral Activation Scale; BH engagement
Perceived social support	Interpersonal Needs Questionnaire; lethal means restriction
Suicide-related impulse control	McCullumsmith et al. (2014)
Implementation outcomes	
Engagement	Session length, number of features used, screens with most user interaction, completeness of templates
Costs	Clinician time spent and associated costs; billability of services

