arm) respectively. To elucidate the impact of intervention components on intervention targets, we will use t tests to compare our three main intervention targets at follow-up (social support, behavioral activation, and impulse control) between those who did and did not receive the intervention component specific to that target, and will use t tests to examine the association between intervention targets and patient outcome (occurrence of any suicidal behavior and presence of active suicidal ideation at follow-up). For all analyses, effect sizes will be estimated, with parametric and non-parametric statistics as appropriate.

Sample size justification. For our development and usability testing, we will engage 12 individuals with lived experience for persona testing in Aim 1 and 12 ED patients for in vivo usability testing in Aim 2. This number was chosen because a sample of 10 users can identify 95% of usability problems¹ including in persons with serious mental illness.² The sample size for the feasibility trial (n=45) is based on the same principle, allocating 15 patients in each of the three arms and allowing for moderate attrition over the three-month follow-up period. Because of the funding mechanism and our focus on platform development, the feasibility trial is **not** powered to test hypotheses but rather to inform the feasibility of the intervention and data collection measure for a future large-scale implementation trial. With significance set at 0.05 and assuming a power of 0.80, a sample size of 45 participants across three arms will allow us to detect a large effect size of $f=0.48$ in usability and acceptability scores and $w= 0.46$ in dichotomous suicidal behavior outcome.

REFERENCES

1. Faulkner L. Beyond the five-user assumption: Benefits of increased sample sizes in usability testing. *Behav Res Methods, Instruments, Comput.* 2003;35(3):379-383. doi:10.3758/BF03195514.

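### Aim 3 calls an unrandomized comparison of component receivers with non-receivers an impact, and tests it without the baseline target score

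*Combined protocol and SAP*

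**What the plan says.** The Aim 3 part of the SAP (section B, Feasibility Trial) states: "To elucidate the impact of intervention components on intervention targets, we will use t tests". The outcome is each of the three targets at follow-up: social support, behavioral activation and impulse control. The grouping is "between those who did and did not receive the intervention component specific to that target". No baseline value, change score or covariate is named. In the same sentence, the tests relating targets to patient outcomes are described only as an association.

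On assignment, section 11 of the protocol says of the 45 patients: "They will be randomized to one of three TASCS App modalities in the ED". All three groups then receive three "counseling calls, access to the TASCS app, and one assessment call in the three months after discharge". The SAP's list of arms repeats the same post-ED elements for each arm.

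The section 11 table that lists the targets is headed "Measures at baseline and follow-up in feasibility trial (Aim 3)". One entry, for example, is the "Drive subscale of the Behavioral Activation Scale".

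The SAP commits to intent-to-treat twice, in its opening section and again in section B, with no exception. Section B also has a covariate rule. Variables that differ between groups, or that matter on theoretical grounds, may enter a multivariate analysis where suitable.

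**The concern.** Impact is a causal word, and nothing supplied supports a causal reading of this comparison. Patients who do and do not receive a component may already differ on the target that the component is meant to change. A difference at follow-up can then be an old difference carried forward, and an old difference in the other direction can hide a real effect. A t test on follow-up scores cannot separate these cases.

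The SAP makes the study of candidate targets one of the purposes of the trial, so these results will be read with interest when the next trial is designed. The stake is the interpretation of an exploratory analysis. The documents give no rule by which these tests choose components for the later trial.

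**Working it through.** **1. The plan's own figures.** The SAP gives detectable effects of f = 0.48 and w = 0.46 for N = 45, three arms, alpha 0.05 and power 0.80. Both reproduce.
- Noncentral F with noncentrality f²N = 0.48² × 45 = 10.4 gives power 0.800.
- Noncentral chi-square on 2 df with Nw² = 45 × 0.46² = 9.5 gives power 0.795; exactly 80% needs w = 0.463.

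These figures concern comparisons of arms. The SAP states none for the receipt t tests. Their detectable difference at 80% power with all 45 followed is 0.85 SD for a 22/23 split and 1.36 SD for 40/5.

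**2. What is randomized.** Delivery mode in the ED is randomized. The post-ED package is common to all arms. Features used, template completeness, calls answered and app sessions are listed in section 11 as things to be measured. No supplied text assigns a patient to go without a component.

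**3. Does the covariate rule cover it?** Its theory limb could admit a baseline target score, but only in a multivariate analysis. The SAP names t tests here, and a t test takes no covariate. The imbalance check behind the rule compares the three treatment groups, not receivers with non-receivers.

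**4. Size, on assumed inputs.** The documents give no baseline gap, no baseline-to-follow-up correlation (rho) and no receipt split. I assume normal data with within-group SD 1, zero component effect and two-sided alpha 0.05. The splits are 40/5, 36/9 and 23/22 of 45 patients, and 29/7 of 36 (20% attrition, an assumed figure).

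The t test rejection rate comes from the noncentral t with noncentrality d × √(n₁n₂/(n₁+n₂)). The multiplier is √(200/45) = 2.11 at 40/5, √(203/36) = 2.37 at 29/7, √(324/45) = 2.68 at 36/9 and √(506/45) = 3.35 at 23/22.

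- Scenario A: the gap acts only through the baseline score, so d = rho × gap.
- Scenario B: the difference is stable over time, so d = gap.

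False-positive rate of the planned t test, %:

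| Scenario | gap | rho | d | 40/5 | 29/7 | 36/9 | 23/22 |
|---|---|---|---|---|---|---|---|
| A | 0.5 | 0.5 | 0.25 | 8.1 | 8.9 | 10.1 | 13.0 |
| A | 0.5 | 0.7 | 0.35 | 11.1 | 12.7 | 15.1 | 20.9 |
| B | 0.5 | any | 0.50 | 17.8 | 21.1 | 25.9 | 37.4 |
| A | 0.2 | 0.5 | 0.10 | 5.5 | 5.6 | 5.8 | 6.2 |
| A | 0.2 | 0.7 | 0.14 | 6.0 | 6.2 | 6.6 | 7.4 |
| B | 0.2 | any | 0.20 | 7.0 | 7.5 | 8.2 | 10.1 |

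**5. The same settings with baseline adjustment** (ANCOVA, simulated with 40,000 runs per cell).
- Scenario A, gap 0.5: bias at most 0.002 SD, rejection 4.7-5.2%.
- Scenario B, gap 0.5: the expected remaining bias is (1 − rho) × gap, that is 0.5 × 0.5 = 0.25 SD or 0.3 × 0.5 = 0.15 SD. In the order of the table's splits, rejection is 8.9, 9.7, 11.3 and 14.5% at rho 0.5, and 7.1, 7.6, 8.3 and 10.2% at rho 0.7.
- Gap 0.2: about 5% in A and 5.4-6.6% in B.

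**6. Precision.** Adjustment also narrows the estimate. The mean 95% CI half-width falls from 0.95 SD to 0.84 (rho 0.5) or 0.70 (rho 0.7) at 40/5, and from 0.60 to 0.54 or 0.45 at 23/22.

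**The case against.** The strongest reply is that too little is known to call this a fault. The SAP defines neither component nor receipt, and the grant pages that the protocol cites for Aim 3 procedures and analysis are not supplied. If receipt of ED content followed the delivery mode, it would be partly randomized. That is possible, but nothing supplied says so. It limits what can be said about the mechanism and direction of bias; it does not support the causal word.

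Baseline collection of each target is indicated, not confirmed. The table headed as baseline and follow-up also lists calls answered, which cannot exist at baseline, and section 11 says that measures beyond Aim 2 are still being developed. Two of the targets have two entries each, so the analysed score must be named. These points stand and make the adjustment conditional. They do not defeat it, because the covariate is the baseline of whichever continuous score the t test would have used.

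The SAP states its grouping openly, so few readers would take it for a comparison of randomized arms. That reduces the intent-to-treat point to a missing label. Effect sizes are already promised for all analyses, though intervals and group sizes are not.

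Finally, the SAP itself says that the pilot lacks the power for hypothesis tests and is meant to prepare a later, larger trial. This limits the weight of the point, but low power does not remove confounding.

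**Conclusion.** The point holds. The supplied text gives no basis for reading the receipt comparison as an impact, and the named test leaves out a baseline score that the plan indicates will be available.

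The actual size is unknown. In the illustration it runs from negligible (5.5% false positives) to serious (37%), depending wholly on the assumed gap, correlation and split. Adjustment is a partial remedy. It removes the part of the selection carried by the baseline score and leaves 0.15-0.25 SD of bias if a 0.5 SD difference is stable.

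The change should be made because it is cheap and prevents a misreading. No primary result depends on it. Confidence is medium, because the definition of receipt and the cited grant pages could not be seen.

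**What to change.** In section B of the SAP:

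- Reword the aim of this analysis as describing an association, and label it exploratory, observational and not intent-to-treat.
- State what counts as receiving each component, and which score is analysed for each target.
- Replace only the component t tests with a linear regression of the follow-up target on receipt, adjusted for the baseline score of that same target. First confirm that this score is collected.
- Report the estimate with a 95% CI, the numbers of receivers and non-receivers, and their baseline target means.
- State that adjustment does not remove selection on unmeasured or stable differences.

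The target-outcome t tests can stay, since the SAP already calls them an association.

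The cost is a few sentences and one degree of freedom per model, with no new data if the baseline scores are collected as indicated. For a target with no baseline score, the adjustment and the baseline means drop out; the relabelling, the definition of receipt and the reporting of group sizes still apply.
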